5.1.7.4.2 Use of Rescue Medication

Rescue medication will be defined as receiving paracetamol (authorized), any other analysis and anti-inflammatory drugs as well as any non-pharmaceutical therapy (prohibited) for treating pain starting from randomization to DAY 5 Visit 2 or starting before the study and still ongoing at randomization. Each use of rescue medication will be classified according to Study Day ([Start date] – [Randomization date] + 1).

The number and percentage of subjects using rescue medication will be presented for treatment groups by Study Day (Starting from Randomization to Day 5 Visit 2, Starting before the Study and still ongoing at Randomization, Day 1, Day 2, Day 3, Day 4, Day 5) and overall.

Summary of Use of Rescue Medication will be based on the Safety population.

Additionally, all medications and non-drug treatments/procedures received on Day 6 will be listed and summarized for the Safety population.

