5.3 Exploratory Objectives

Exploratory objectives for this study include:

- To assess the frequency and use of rescue medication
- To assess the subject evaluations of least, average, and worst pain

6 Study Design

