7.6.2 Day 1 to Day 5, At Home

The following procedures will take place while subjects are at home:

- Completion of the e-diary in the morning (e.g. 8:00 [use 24 hr time format]) (this is not applicable at Day 1)
 - o Pain perception (using NRS)
 - Instantaneous: pain at the moment of the evaluation
 - Average pain in the previous 12 hours.
 - Worst pain in the previous 12 hours
 - Least pain in the previous 12 hours
 - o Pain relief (Using VRS) for the question "Do you feel pain relief?" 0= 'none', 1= 'slight', 2= 'moderate', 3= 'lots', 4= 'complete'.
 - o Is the Pain acceptable (binary, Yes/No)?
 - Need of rescue medication (time and dose)
- Completion of the diary in the evening (e.g. 20:00 [use 24 hr time format]) (this is not applicable at Day 5)
 - o Concomitant therapies, if any
 - Daily activities to include showers, physical activities, sporting activities, etc.
 - o Pain Perception (using NRS)
 - Instantaneous: pain at the moment of the evaluation
 - Average pain in the previous 12 hours.
 - Worst pain in the previous 12 hours
 - Least pain in the previous 12 hours
 - o Pain relief (Using VRS)
 - o Is the Pain acceptable?
 - Need of rescue medication (time and dose)
 - Adverse events
 - Need of patch removal and application of a new patch according to instructions for use (Section 17.3) and recording of reason.

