3.4 Analysis Timepoints for e-diary Questionaries

The analysis timepoints will be derived for questionaries collected via e-diary (for an extract based on Data Export Specification 2.0) as defined in Table 3.

The study day will be calculated as the following:

$$Study Day = (Completed Date) - (Randomization Date) + 1.$$

Adverse events, medication usage and patch application data collected via e-diary will not be used for analysis. Those are being transcribed by the site from the diary into the CRF database that will be used for analysis.

In consistency with Section 3.1, assessments collected at Day 1 Visit 1 will be considered as the baseline (if for FIRTECH Patch arm the assessment was done before the Patch application). Analysis timepoints "Baseline" and "Day 5 Visit 2" are derived only for on-site evaluations.

CONFIDENTIAL Page 14 of 30

Table 3: Analysis Timepoints for eDiary

Study Day	Questionnaire Name	Analysis Timepoints
Day 1ª	Daily Diary (Visit 1 Day 1) or Evening Daily Diary when Protocol Deviation (PD) comment completed as mentioned in the NTF number: 019, dated 22 Nov 2022 and when the associated PD occurrence date is equal to the CRF Visit 1 date.	Baseline
Day 1	Roland-Morris Disability Questionnaire	Baseline
Day 1	Evening Daily Diary	Day 1 Evening
Day 2	Morning Daily Diary	Day 2 Morning
Day 2	Evening Daily Diary	Day 2 Evening
Day 3	Morning Daily Diary	Day 3 Morning
Day 3	Evening Daily Diary	Day 3 Evening
Day 4	Morning Daily Diary	Day 4 Morning
Day 4	Evening Daily Diary	Day 4 Evening
Day 5	Morning Daily Diary	Day 5 Morning
Day 5 ^a	Daily Diary (Visit 2 Day 5) or	Day 5 Visit 2
	Morning Daily Diary when PD comment completed as	
	mentioned in the NTF number: 019, dated 22 Nov	
	2022 and when the associated PD occurrence date is	
	equal to the CRF Visit 2 date.	
Day 5	Roland-Morris Disability Questionnaire	Day 5 Visit 2

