5.1.5 Prior and Concomitant Medications

Medications will be coded with the WHO drug dictionary (WHO Drug global B3 September 2021), listed and presented by ATC Class 2 and Preferred Term (PT) for Safety population by treatment group and overall.

If a medication cannot be found in WHO dictionary, it will be coded as "WHO Code Not Defined".

CONFIDENTIAL Page 18 of 30

Private and Confidential Study No LPS16453 Date: DEC 12, 2022

Each medication will be classified as prior, concomitant or both.

Any medication taken within 4 weeks (28 days) before the first patch application (for the FIRTECH Patch treatment group) or randomization (for the No Patch treatment group) will be considered as prior.

Any medication taken on or after the first patch application (for the FIRTECH Patch treatment group) or randomization (for the No Patch treatment group) or with a start date prior to and ongoing at the time of the first patch application (for the FIRTECH Patch treatment group) or randomization (for the No Patch treatment group) will be considered as concomitant.

In case when start/stop date is incomplete, or medication is ongoing, the following assumption will be made for Prior/Concomitant classification:

- If there is reasonable possibility that medication was taken within 4 weeks (28 days) before the first patch application (for the FIRTECH Patch treatment group) or randomization (for the No Patch treatment group), the medication will be considered as prior;
- If there is no evidence that medication was taken before the first patch application (for the FIRTECH Patch treatment group) or randomization (for the No Patch treatment group), medication will not be classified as prior;
- If there is a reasonable possibility that medication was taken on or after the first patch application (for the FIRTECH Patch treatment group) or randomization (for the No Patch treatment group) and there is no evidence that medication intake was stopped prior to, then medication will be classified as concomitant.

Prior medications will be summarized and listed with ATC Class 2 and PT for Safety population by treatment group and overall.

Concomitant medications will be summarized and listed with ATC Class 2 and PT for Safety population by treatment group and overall.

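### The Day 1–5 rows of the rescue-medication table count uses that started on each day, not subjects using rescue on that day, and the table reports no intakes or days of use

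*SAP*

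**What the plan says.** SAP 5.1.7.4.2 counts as rescue any paracetamol, prohibited drug or non-pharmaceutical therapy given for pain. The use must either begin between randomisation and the Day 5 visit, or begin before the study and still be ongoing at randomisation. The day is then assigned as follows: "Each use of rescue medication will be classified according to Study Day", computed as start date minus randomisation date plus one. No stop date enters the rule.

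On the display, the same section says: "The number and percentage of subjects using rescue medication will be presented for treatment groups by Study Day". The first row covers any start from randomisation to the Day 5 visit. The remaining rows are "Starting before the Study and still ongoing at Randomization, Day 1, Day 2, Day 3, Day 4, Day 5) and overall". The table (14.1.3.3) uses the Safety population, and Listing 16.2.4.4.3 lists rescue use.

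The purpose is set in Protocol 5.3: "To assess the frequency and use of rescue medication". Protocol 6.3.3 and SAP 2.2.3 name frequency of use as the endpoint, and Protocol 8.3.1.3 plans a descriptive analysis from the diary. The twice-daily diary in Protocol 7.6.2 has the item "Need of rescue medication (time and dose", and Protocol 7.6.1 asks subjects to record when each intake occurred and how much was taken.

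SAP 3.4 does not analyse the diary's medication data directly: "Those are being transcribed by the site from the diary into the CRF database that will be used for analysis". SAP 5.1.5 shows that medication records in that database can span time, since it has a rule for the case "In case when start/stop date is incomplete, or medication is ongoing".

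**The concern.** The row label and the derivation describe different quantities. A reader of a row for Day 3 will take it as the proportion of subjects who used rescue on Day 3. The rule delivers the proportion who have a record that began on Day 3.

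The two agree when every record lasts one day. They separate when a record covers several days, and when use was already under way at randomisation. If sites enter courses, a subject who takes paracetamol on all five days and a subject who takes it once on Day 1 look the same in the day rows: one count on Day 1 and nothing afterwards.

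This deserves attention even in an exploratory table. The trial is open label, absence of rescue is part of the primary response, and the full analysis set removes rescue users from the secondary analyses. Table 14.1.3.3 is therefore the main planned summary of how rescue behaviour differed between arms. The day rows are the only part of it that could show persistent against isolated use. The table also gives numbers of subjects only, so a reader cannot learn how often, or on how many days, users took rescue.

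**Working it through.** The plan states no figure on this point, so there is nothing to reproduce. The check applies the SAP rule to constructed records.

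**1. The formula.** Study Day = start date − randomisation date + 1. A start on the randomisation date gives 0 + 1 = 1. A start on the day before gives −1 + 1 = 0. A use that began before the randomisation date and is ongoing therefore has Study Day 0 or less and matches no Day 1–5 row. It is counted in its own row and overall.

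**2. Five invented users.** A uses rescue on Days 2–4 (one record). B has use ongoing from before randomisation to Day 5 (one record). C uses it on Day 1 only. D uses it on Days 3 and 5 (two records). E uses it on Days 1–5 (one record).

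| Row | SAP rule (start day) | In use on the day (start ≤ day ≤ stop) |
|---|---|---|
| Day 1 | 2 (C, E) | 3 (B, C, E) |
| Day 2 | 1 (A) | 3 (A, B, E) |
| Day 3 | 1 (D) | 4 (A, B, D, E) |
| Day 4 | 0 | 3 (A, B, E) |
| Day 5 | 1 (D) | 3 (B, D, E) |
| Ongoing at randomisation | 1 | 1 |
| Any start from randomisation | 4 | 4 |
| Overall | 5 | 5 |

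The three summary rows do not change. If each day of use is its own record, including dated intakes for B, the SAP rule itself gives 3, 3, 4, 3, 3.

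**3. Size by record length.** Assume one record of L days per user, starts spread evenly over Days 1–5, and courses cut at Day 5. The day rows then count 5 starts. Subject-days of use are the sum over start days s = 1 to 5 of min(L, 6 − s).

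| L | Subject-days of use | Captured by day rows |
|---|---|---|
| 1 | 5 | 5/5 = 100% |
| 2 | 2+2+2+2+1 = 9 | 5/9 = 56% |
| 3 | 3+3+3+2+1 = 12 | 5/12 = 42% |
| 4 | 4+4+3+2+1 = 14 | 5/14 = 36% |
| 5 | 5+4+3+2+1 = 15 | 5/15 = 33% |

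**4. Which L applies.** The documents do not state the CRF record unit. The diary instructions point towards separate intakes. The ongoing-at-randomisation category (SAP 4.1.3 and 5.1.7.4.2) shows that at least some rescue records are expected to extend over time, because a single dated intake cannot be ongoing.

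**5. Other uses of the definition.** The responder definition (SAP 5.1.7.1) and the full analysis set (SAP 4.1.3) both depend on any rescue use. Neither reads the day rows.

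**The case against.** The best defence is that the problem may never arise. Subjects record each intake with time and dose, sites transcribe those entries, and the SAP speaks of each use. If one record is made per day of use, the start day is the day of use and the dated-use rows are correct. SAP 5.1.5, which allows for ongoing records, covers all medications and not rescue in particular. This stands as far as it goes: the documents leave the record unit open, so the loss could be nil for dated use.

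Use ongoing at randomisation should also be uncommon, because exclusion criteria 8, 9 and 12 in Protocol 6.4.6 bar recent pain medication and recent non-pharmaceutical treatment. It is not lost from the table either, since it has its own row. Both points stand, but the plan provides for the category and still leaves it out of every day row.

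Some stronger readings are tempting and are not supported:

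- A reader might infer that the rescue objective as a whole is answered wrongly. The any-start, ongoing and overall proportions are right.
- A reader might infer that the rule forces a decline from Day 1 to Day 5. It does so only if starts cluster early. With even starts the rows are flat, and the constructed example gives 2, 1, 1, 0, 1.
- A reader might quote an 80% undercount, from 1 of 5 days counted. That needs a full Day 1–5 course held in one record for every user.

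Lastly, counting every day from start to stop can err the other way, if a site enters intermittent as-needed use as one range. That is fair, and it shapes the fix.

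**Conclusion.** The point holds in limited form. The Day 1–5 rows count starts while being labelled as use. Multi-day records are missing from their later days, and records ongoing from before the randomisation date are missing from all five day rows.

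How much is lost rests on the CRF record unit, which is not stated. Under the assumptions of even starts and courses cut at Day 5, the day rows capture between 100% (1-day records) and 33% (5-day records) of subject-days of use, with 56% at two days. Separately, and whatever the record unit, the table reports neither intakes nor days of use, so the frequency-of-use endpoint is only partly met.

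A reader might go on to infer a threat to the primary result. The documents do not support that: response and full-analysis-set membership both turn on any rescue use. The table is descriptive, exploratory and untested, and the planned listing would allow a reconstruction by hand. Severity is minor.

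**What to change.** In SAP 5.1.7.4.2:

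- State whether a CRF rescue record is an intake, a day or a course.
- Count a subject as a user on each study day with a dated intake. Where only a start–stop range exists, count each day from the later of start and randomisation to the earlier of stop and the Day 5 visit, including records ongoing at randomisation.
- Add, by arm, the number of days with rescue use and the number of intakes per subject.
- Keep the any-start, ongoing and overall rows unchanged.

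If the derivation is left as it is, the least that is needed is to label the day rows as uses started on that day.

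The cost is a small derivation change and two summary rows from data the diary already collects. No test changes. There are two downsides. Intermittent use entered as one range may be overcounted, which is why dated intakes should take precedence. And if the CRF does not hold single intakes, counting them means using diary entries that SAP 3.4 now sets aside, so that section needs an exception and the diary entries must be compared with the transcribed records.

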5.1.7.5 Compliance Analysis

5.1.7.5.1 eDiary Compliance (%)

eDiary Compliance will be measured based on the number of completed e-Diaries out of 12 (10 for pain perception and 2 for RMDQ). A subject will be considered as compliant if at least 80% of eDiaries are completed, otherwise, if less than 80% of eDiaries are completed, a subject will be considered as non-compliant.

The number and percentage of compliant and non-compliant subjects will be presented along with the descriptive summary of eDiary Compliance (%) for treatment groups.

CONFIDENTIAL Page 23 of 30

Summary of eDiary Compliance will be based on the Safety population.

5.1.7.5.2 Patch Use Compliance

Patch use compliance will be measured based on the number of days the subject wears a FIRTECH patch without reapplication (duration of wearing the patch after the first application till the first removal). Subject will be considered as patch use compliant if the first patch is worn at least for 4 days. Otherwise, subject will be considered as non-compliant.

The number and percentage of compliant and non-compliant subjects will be presented along with descriptive summary of Patch Use Compliance (Days) and number and percentage of subjects from following Patch Use Compliance categories:

• 1 day;

• 3 days;

• 5 days;

• 2 days;

• 4 days;

• > 5 days.

Summary of patch use compliance will be based on the Safety population.

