4.4 Device Disposition

At the end of the study period, the Subject will return to the investigational site to have the patch removed. If the patch is removed or if it peels off prior to its scheduled removal, Subjects are instructed to apply a new patch at home. All the used and unused patches have to be returned to the investigational site at Visit 2

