7.6 Clinical Procedures

The study will be performed in Investigational Sites and an online e-diary will be used.

A total of 2 site visits and 1 phone contact are planned during a maximum of 5 days of treatment and 6 days of total study duration.

7.6.1 Day 1, Visit 1

Clinical procedures on Day 1, Visit 1 include the following:

- Verification of eligibility
- Informed Consent Signatures
- Local Physical Examination

- Collection of Vital Signs to include: Respiratory rate, Heart rate, Temperature, Blood Pressure
- Collection of Demographics to include: Age, Gender
- Collection of relevant medical history and concomitant medications
- On-line daily e-diary will be explained and activated
- Urine pregnancy testing (for women of childbearing potential only)
- Causes and/or circumstances triggering the acute back pain
- Baseline Subject symptom self-assessment
 - Pain Perception (NRS): Numerical Rating Scale^[3] for pain assessments at baseline and at defined time points: 0-10 NRS; '0' representing "no pain" and '10' representing "worst pain imaginable
 - Instantaneous: pain at the moment of the evaluation
 - Average pain in the previous 12 hours.
 - Worst pain in the previous 12 hours
 - Least pain in the previous 12 hours
 - o Roland-Morris Disability Questionnaire (RMDQ)^[5]
- Baseline mobility assessment (physician)
- Randomization:
 - O Arm A: ITP FIRTECH: Patch application according to the instruction for use in Section 17.3: The patch has to stay in position for 5 days. If the patch is taken-off or if it fell off during the study duration, the subject is invited to replace the patch at home following the instruction for use. Subject is allowed to take-off the patch at any time in case of severe skin itchiness, irritation, or skin reaction and in this case the subject has to contact the study center.
 - o Arm B: no-patch: Subjects will be informed that they will not be assigned a patch in this study.
- All subjects are informed that rescue mediation (paracetamol, up to 2 g per day), while not encouraged, is allowed if necessary.
- All subjects will be informed of the prohibited medications.
- If rescue medication is taken, the exact moment(s) and the dose(s) have to be indicated in the e-diary.
- An explanation will be provided on how to use e-diary at home and providing all necessary access credentials
- All subjects will be requested to avoid bed rest and will be recommended to continue with a normal daily life activity.

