7.8 Study Timetable / Schedule of Events

Table 3. Schedule of Events

Visits	V1	At	V2	Phone	Unsch	Notes
		Home		Call		
Days	D1	D1 to	D5	D6		
		D5				
Eligibility verification	✓					
Informed Consent	✓					
Demographics /	✓					
Medical History						
Physical Exam	✓		✓		✓	
Vital Signs	✓				✓	

Visits	V1	At	V2	Phone	Unsch	Notes
		Home		Call		
Days	D1	D1 to D5	D5	D6		
Urine Pregnancy Test	√					For women of child-bearing potential only
E-diary Activation	✓					
Randomization	✓					
E-diary Completion	✓	√ *	√ **			*2 times per day at the same times **On-site evaluations
Pain perception	✓	✓	✓			
Pain-relief evaluation		✓	✓			
Pain acceptable perception		~	√			
Rescue Medication Needed		V	√			
Roland-Morris Disability Questionnaire	√		√			
Mobility assessment	√		√			Schober's Test or Fingertip- to-floor test
Adverse Event assessment	√	~	√	√	√	
Patch application / removal	✓		✓		✓	Patch(es) has(have) to be used for 5 days. If the patch is taken-off for a safety reason, the subject has to contact the study center. If the patch falls off, the subject has to replace it as soon as possible. The subject will complete the diary card, informing about the patch replacement, the reason of change, and the time spent with no patch.
Concomitant therapies	✓	✓	✓	✓	✓	
e-diary review			√		√	

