8.3.1.4.2 Patch use Compliance (Days)

Patch Use Compliance will be measured based on the number of days subject wears a patch. Subject will be considered as compliant if a patch is worn at

least for 4 days. Otherwise, if less subject wears a patch for less than 4 days, subject will be considered as non-compliant.

Descriptive analysis will be conducted for Patch Use Compliance (Days), as well as Patch Use Compliance (Days) will be summarized in categories: "1 day", "2 days", "3 days", "4 days", "5 days" and ">5 days" using frequency tables. The number and percentage of compliant and non-compliant subjects will be presented as well, using the ITT paradigm (i.e. as randomized).

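### The SAP measures patch compliance on the first patch only, so some subjects who replace a lost patch as instructed and reach 4 days of wear are reported as non-compliant, and SAP 5.1.11 does not declare the change from the protocol

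*SAP*

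**What the plan says.** **Protocol.** Section 8.3.1.4.2 defines the measure: "Patch Use Compliance will be measured based on the number of days subject wears a patch". The threshold is 4 days, and the complement is worded the same way: "Otherwise, if less subject wears a patch for less than 4 days" leads to the label non-compliant. Nothing there restricts the count to the first patch.

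The protocol expects patches to be replaced. Section 4.4, on a patch that is removed or peels off early: "Subjects are instructed to apply a new patch at home". The Visit 1 procedures in 7.6.1: "the subject is invited to replace the patch at home following the instruction for use", with two extra patches handed out. The schedule of events in 7.8: "If the patch falls off, the subject has to replace it as soon as possible". The instructions for use in 17.3 say the second patch goes on the same area.

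**SAP.** Section 5.1.7.5.2 counts wear without reapplication, explained as "duration of wearing the patch after the first application till the first removal". The rule is: "Subject will be considered as patch use compliant if the first patch is worn at least for 4 days". Everyone else falls under: "Otherwise, subject will be considered as non-compliant".

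**Declared changes.** For patch compliance, SAP 5.1.11 lists only the move from the ITT to the Safety population. The change of definition is not listed.

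**The concern.** The two documents define different variables under one name. The protocol's variable is how long the subject wore a patch. The SAP's variable is how long the first patch stayed on, which depends largely on adhesion.

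A subject can follow every instruction, lose the first patch early, replace it at once, complete the wear period, and still appear in the non-compliant row. A reader of Table 14.1.3.1 would take that row as a statement about adherence. Because 5.1.11 does not mention the change, a reader who compares the report with the protocol gets no warning that the measure differs.

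**Working it through.** The plan states no figure for this measure, so there is none to reproduce. The check sets the two rules side by side and classifies the same subjects under each.

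**Inputs**
- Threshold: 4 days in both documents (protocol 8.3.1.4.2, SAP 5.1.7.5.2).
- Wear period: application on Day 1, removal at Visit 2 on Day 5 (protocol 7.6.1, 7.6.3).
- Protocol measure: days with a patch on, all patches together.
- SAP measure: first application to first removal.

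**Step 1: direction of the difference.** First-patch wear is part of total wear, so first-patch wear ≤ total wear for every subject. Anyone compliant under the SAP is therefore compliant under the protocol. The rules can disagree in one direction only: compliant by the protocol, non-compliant by the SAP.

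**Step 2: worked classification.** Suppose the first patch comes off on Day k, is replaced the same day, and wear continues to Day 5. On a calendar count, with Day 1 counted as 1, first-patch wear is k and total wear is 5.

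| First patch off | First-patch days | SAP label | Total days | Protocol label |
|---|---|---|---|---|
| Day 1 | 1 | non-compliant | 5 | compliant |
| Day 2 | 2 | non-compliant | 5 | compliant |
| Day 3 | 3 | non-compliant | 5 | compliant |
| Day 4 | 4 | compliant | 5 | compliant |
| Day 5 | 5 | compliant | 5 | compliant |

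The labels differ for loss on Days 1 to 3 and agree from Day 4.

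**Step 3: not every early replacement is affected.** If the first patch comes off on Day 1 and is not replaced until Day 4, the days with a patch are 1, 4 and 5, a total of 3. That is non-compliant under both rules. Two spares are supplied, so one subject can also have two early replacements and still be one subject in the table.

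**Step 4: the day count matters.** Neither document says whether days are calendar or elapsed. On an elapsed count, Day 1 to Day 5 at the same clock time is 5 − 1 = 4 days. First-patch wear is then k − 1, so the SAP rule also fails a first patch lost on Day 4 (3 elapsed days). Continuous wear can itself fall short: applied at 14:00 on Day 1 and removed at 10:00 on Day 5 is 10 + 72 + 10 = 92 hours, and 92/24 = 3.83 days. An elapsed count would therefore label some subjects non-compliant under either definition, with no patch lost.

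**Step 5: size in the table.** With 200 randomized 1:1, the patch arm has 200/2 = 100 subjects. If all have the device applied, each subject in the disagreement group lowers the reported compliance rate by 1/100 = 1 percentage point. The documents give no rate of early patch loss or replacement, so the number of such subjects is unknown.

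**Step 6: where the variable is used.** None of the five analysis populations in SAP 4.1 refers to patch compliance. The primary and secondary analyses contain no compliance term, and 5.1.9 rules out subgroups. Adverse events are counts and percentages of subjects in the Safety population (5.1.8.1), with no exposure-time denominator. Exit for non-compliance under protocol 6.4.7 points to 7.9, which covers visits and diary entries only. What remains is the summary in Table 14.1.3.1.

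**The case against.** **The protocol wording is loose.** Its 4-day threshold speaks of a patch in the singular, 7.6.1 says the patch is to stay in place for 5 days, and the protocol leaves analysis detail to the SAP. The first-patch rule could be a deliberate refinement. This stands in part: the SAP rule is explicit, not a slip of the pen. But the protocol's measuring sentence is about days the subject wears a patch, and its replacement instructions fit total wear. A deliberate change belongs in 5.1.11, which does list smaller ones.

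**The impact is descriptive only.** This stands in full and limits the weight of the point.

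**Patch data are reported anyway.** The title of Table 14.1.3.1 covers patch application as well as compliance, and Listing 16.2.5 shows patch application. A listing does not correct the headline percentage, however, and the table layouts are not in the documents.

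**Total wear may not be derivable exactly.** Protocol 7.8 has the subject record time with no patch in the diary, but SAP 3.4 says patch data in the e-diary are not analysed, only what the site transcribes to the CRF. The diary items in 7.6.2 name removal, new application and reason, not time off. The documents do not show that time off reaches the CRF. This also stands, and the fix allows for it.

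**Stronger readings that the documents do not support.** A reader might infer that safety exposure is understated. It is not, because no safety analysis uses wear days, and treatment-emergent status runs from first application without ending at first removal. A reader might also infer that every replacement is a misclassified subject; Steps 2 and 3 show otherwise. A figure such as 20–40% early replacement would be an assumption with no source in either document.

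**Conclusion.** The discrepancy is real and undeclared. SAP 5.1.7.5.2 reports first-patch duration under the name of patch use compliance, and so labels as non-compliant any subject whose first patch came off before 4 days but whose total wear reached at least 4. The error runs one way: reported adherence can only be lower than under the protocol measure.

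The size is one percentage point per affected subject in a patch group of about 100, with the number affected unknown. The consequence is limited to one descriptive summary. It does not touch the primary result, the key secondary tests, any analysis population or the adverse event rates.

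The conclusion assumes that the protocol's measure means total wear over all patches, which its measuring sentence and replacement instructions support. The Day 1 to 3 boundary assumes calendar days and same-day replacement.

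**What to change.** - In SAP 5.1.7.5.2, define compliance as the number of calendar study days with any FIRTECH patch in place, across all patches, derived from the CRF patch application data. Keep the protocol's 4-day analysis threshold.
- State the calendar count explicitly, so that a subject with uninterrupted wear from Day 1 to Visit 2 cannot fall below 4 through clock times.
- Subtract time without a patch if that item is transcribed to the CRF. If it is not, say so and derive the days from the recorded application and removal dates.
- Report first-patch duration as a separate row, labelled as an adhesion measure.
- If the sponsor prefers to keep the first-patch definition, relabel it as first-patch duration and declare and justify it in 5.1.11.

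The cost is a SAP wording change, some added derivation work and one extra summary row. No new data collection is needed for the calendar count, provided that the CRF holds application and removal dates for each patch; the sponsor should confirm this.
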